3.5 Potential Risks

3.5.1 Potential risks for intravenous (IV) catheter placement

Placement of the intravenous catheter can cause a brief, generally mild period of pain lasting for a few seconds at the site of catheter placement. There is the potential that the first attempt at venous cannulation will be unsuccessful and the patient will require multiple attempts to place the IV. Intravenous catheter placement can cause a bruise, though in patients without known bleeding diathesis this is usually mild and self-resolving. Some individuals experience dizziness or lightheadedness. Other complications are rarer. Infection from a cleanly-placed IV is rare, especially given the short anticipated duration of catheter retention. There is the chance of the catheter becoming dislodged from the vein and infiltrating the contents flowing through it into the muscle or subcutaneous fat. As only a minimal amount of fluid will flow through the vein and no caustic or vasoactive substances will be used (except in the case of a rare, potentially serious adverse event), this presents no risk to the volunteer.

3.5.2 Potential risks from lumbar puncture

Lumbar Puncture (LP) is widely used technique of CSF sample aspiration by thin needle from the subarachnoid space of the lumbar dural sac. LP is a major diagnostic tool used in neurological clinics as relatively safe method to obtain CSF sample for further analysis. The important complication of LP is post-lumbar puncture headache (PLPH) developing within a week after LP. In a multisite international trial, 9% of 3868 enrolled patients reported PLPH,⁴⁰ with 0.3% patients requiring an epidural blood patch (procedure of introducing autologous blood into epidural space). Other adverse events were non-specific headache (10.2%), back pain (17%), nausea and/or vomiting (2.5%), dizziness (4.5%) (1.3%). Other possible complications may include bleeding as well as temporary or permanent neurological damage, although these are extremely rare. Management of these potential adverse events are described below in section 3.4.

3.5.3 Potential risks from blood collection

The total amount of blood collected during each study visit is approximately 60 mL (about 10% of a standard blood donation), which should not have adverse physiological effects. As described above, the IV catheter placement necessary for blood draws may cause bleeding, bruising, pain, dizziness/lightheadedness, or (very rarely) infection.

3.5.4 Potential risks from ondansetron

Ondansetron is a widely-used drug approved for prevention of chemotherapy-induced, radiotherapy-induced, and postoperative nausea and vomiting. It is commonly used off-label for treatment of nausea and vomiting. The most common reported side effects (~10%) include headache, constipation, and fatigue. Less common (<10%) include drowsiness, diarrhea, fever, anxiety, transient liver enzyme increases, or burning at

injection site. Rare side effects (<1%) include cardiac arrhythmias, ECG changes, dry mouth, anaphylaxis, transient blindness, and hypokalemia.

The FDA has issued a drug safety communication regarding the risk of QTc prolongation and potential progression to torsades de pointes. The risk of cardiac side effects was determined to be dose-dependent with a maximum QTc prolongation by 20msec after 32mg IV administration; consequently, 32mg IV doses are no longer approved. 16mg IV infusion doses (as proposed in this study) are still approved and frequently used for chemotherapy-induced nausea and vomiting. Risk of arrhythmia is increased by comorbidities including: congenital long QT syndrome, congestive heart failure, bradycardias, or patients taking concomitant medications that prolong the QT interval. All such patients would be excluded by our proposed exclusion criteria. Additionally, in our recent study, none of the 15 subjects who received 16mg intravenous ondansetron (meeting the same inclusion/exclusion criteria as in this study), experienced arrhythmias or any other serious side effects (NCT02901054).

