Inclusion and Exclusion Criteria	
Inclusion criteria:
 
 1. Age 18-70; 2. Documented diagnosis of neuropathic pain due to damage or disease affecting the peripheral nervous system; 3. At least Probable neuropathic pain grading¹; 4. Pain duration >3 months; 5. Average pain intensity ≥4 on 0-10 numerical rating scale (NRS). 
Exclusion criteria:
 
 1. Current pregnancy or lactation; 2. Moderate-severe kidney or liver dysfunction; 3. Active cardiac arrhythmias (non-sinus rhythm), Long QT syndrome, or QTc interval >450msec; 4. Congestive heart failure 5. Abnormal troponin values at screening visit; 6. Current treatment with MAO inhibitors, mirtazapine, SSRI or SNRI antidepressants, except duloxetine up to 60mg/day, escitalopram up to 10mg/day, or citalopram up to 20mg/day; 7. Current treatment with tapentadol, tramadol, or fentanyl; 8. Current treatment with P-glycoprotein substrate drugs with narrow therapeutic window, e.g. digoxin; 9. Current treatment with tricyclic antidepressant medications (e.g. amitriptyline, desipramine, imipramine) at a dose >25mg/day; 10. Ongoing use of any of the following medications with known effects on Pgp function: carbamazepine, phenytoin, phenobarbital, cyclosporine, clarithromycin, erythromycin, ritonavir, verapamil, rifampicin, St. John's wort; 11. Current treatment with QT-prolonging drugs, and drugs known to have a significant interaction with ondansetron or other P-glycoprotein substrates (see section 2.3.3.);

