2.3.3 Exclusion Criteria

Participants will not be enrolled if any of the following criteria exist:

1. Current pregnancy or lactation;
2. Moderate-severe kidney or liver dysfunction;
3. Active cardiac arrhythmias (non-sinus rhythm), Long QT syndrome, or QTc interval >450 msec;
4. Congestive heart failure
5. Abnormal troponin values at screening visit
6. Current treatment with MAO inhibitors mirtazapine, SSRI or SNRI antidepressants, except duloxetine up to 60mg/day, escitalopram up to 10mg/day, or citalopram up to 20mg/day;
7. Current treatment with tapentadol, tramadol, or fentanyl
8. Current treatment with P-glycoprotein substrate drugs with narrow therapeutic window, e.g. digoxin.
9. Current treatment with tricyclic antidepressant medications (e.g. amitriptyline, desipramine, imipramine) at a dose >25 mg/day
10. Ongoing use of any of the following medications with known effects on Pgp function: carbamazepine, phenytoin, phenobarbital, cyclosporine, clarithromycin, erythromycin, ritonavir, verapamil, rifampicin, St. John's wort;
11. Current treatment with QT-prolonging drugs, and drugs known to have a significant interaction with ondansetron or other P-glycoprotein substrates (see below):
 - Antiretrovirals of Protease inhibitor (e.g. Ritonavir, Saquinavir) or Non-nucleoside reverse transcriptase inhibitors (e.g. Efavirenz, Zidovudine) family.
 - Phenytoin, Carbamazepine, Oxcarbazepine, Rifampin
 - Amiodarone
 - Azole antifungals (e.g. Itraconazole, Fluconazole)
 - Macrolide antibiotics (Erythromycin, Clarithromycin)
 - Cimetidine
 - Lithium
 - Methylene Blue
 - Non-DHP calcium channel blockers Verapamil and Diltiazem
 - First generation antipsychotic medications Thioridazine, Haloperidol, Chlorpromazine, and Pimozide
 - Second generation antipsychotic medications Ziprasidone and Quetiapine
 - Antihistamine Terfenadine,
 - Antidepressants Trazodone and Bupropion
 - Antiarrhythmics Propafenone, Flecainide, and Procainamide
 - Fluoroquinolone antibiotics Norfloxacin, Ofloxacin, and Ciprofloxacin
 - Cisapride
 - Other strong inhibitors or inducers of Cytochromes P450 2D6 or 3A4.
 - Other strong inhibitors or inducers of P-glycoprotein

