3.6.1 Prevention, diagnosis and management of ondansetron-associated arrhythmia

To minimize the risk of ondansetron-associated arrhythmia, subjects will have a 12-lead ECG performed at the screening visit. Subjects with QTc>450msec or any arrhythmia will be excluded. Potential subjects that would be at elevated risk of developing ondansetron-associated arrhythmia (e.g., current use of QT-prolonging medication) are ineligible for this study. The ondansetron dose used (16mg IV infused over 15min) is approved and commonly used with chemotherapy. Subjects will be monitored with telemetry from the beginning of drug infusion until 2 hrs after infusion is complete. If arrhythmias or prolonged QT develop at any time during the study, subjects will be immediately assessed by a physician. If ECG abnormalities are mild (e.g., infrequent premature atrial/ventricular contractions or QTc>450ms but <500ms), subjects will be monitored in the pain management center by nursing and medical personnel for at least 4 hrs. If the signs/symptoms meet the severity criteria described in Section 3.2 ("Premature discontinuation of protocol for a single patient"), the patient will be withdrawn from the study and sent to the Barnes-Jewish Hospital emergency department (ED) for further evaluation, including cardiology consultation or hospital admission, as needed.

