Epidural blood patches are commonly performed by our Acute Pain Service. Sterile technique (including chlorhexidine swabs, caps, masks, and sterile gloves) is used at all steps by all personnel involved. First, the epidural space is located using a standard Tuohy needle and loss-of-resistance technique. Next, 20ml of the subject's blood is drawn and then injected through the Tuohy needle. Injection is stopped if the subject complains of pressure or paresthesia that could indicate compression of the cauda equina.

3.6.3 Prevention of drug-drug interactions between study drugs and concomitantly used antidepressants

Citalopram, Escitalopram and Duloxetine are not known to produce clinically meaningful interactions when combined with potent P-gp or CYP3A4 inhibitors. When tested specifically in combination with P-gp inhibitors such

as simeprevir, cyclosporine, and verapamil, meaningful interactions were NOT identified for escitalopram and duloxetine⁴⁴⁻⁴⁶. Given that tariquidar is a selective P-gp inhibitor (and possibly weak CYP3A4 inhibitor), we do not expect any meaningful interactions with citalopram, escitalopram, or duloxetine.

Table 3 outlines the potential of drug interactions between SSRI/SNRI antidepressants in the context of use with P-gp inhibitors, and served as a basis for inclusion/exclusion of particular SSRI/SNRI antidepressants.

Table 3. Potential of drug interactions between SSRI/SNRI antidepressants and P-gp inhibitors.

SSRI	FDA-approved maximum dose (mg/day)	Known P-gp substrate	Known CYP3A4 substrate	Known / Clinically relevant interactions with other P-gp inhibitors	Clinically-relevant interactions with CYP3A4 inhibitors	Comments on QT interval prolongation
Citalopram	40	No ^{47,48}	Yes, CYP3A4 and CYP2C19 ⁴⁹	None found (extensive search in PubMed, Lexi-Comp, and IBM Micromedex)	No. ketoconazole co-administration did not significantly affect the pharmacokinetics of citalopram [1]	Dose-dependent QT prolongation ^{47,50}
Escitalopram	20	No ^{48,51}	Yes, CYP3A4, CYP2D6, and CYP2C19	None found (extensive search in PubMed, Lexi-Comp, and IBM Micromedex) ⁴⁹	No. Administration of ritonavir (potent CYP3A4 inhibitor) did not affect the pharmacokinetics of Escitalopram ⁵²	No clinically relevant QT prolongation vs placebo ⁵²

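### Section 3.5.4 says all patients with bradycardias or on QT-prolonging drugs are excluded, but the numbered criteria do not exclude sinus bradycardia and they admit citalopram up to 20 mg/day

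*Combined protocol and SAP*

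**What the plan says.** Section 3.5.4 states: "Risk of arrhythmia is increased by comorbidities including: congenital long QT syndrome, congestive heart failure, bradycardias". It adds patients on concomitant QT-prolonging drugs, and then says: "All such patients would be excluded by our proposed exclusion criteria".

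Exclusion criterion 3 in section 2.3.3 reads: "Active cardiac arrhythmias (non-sinus rhythm), Long QT syndrome, or QTc interval >450 msec". The synopsis has the same criterion. Criterion 4 excludes congestive heart failure. Criterion 11 bars current QT-prolonging drugs and gives an itemised list that does not name citalopram. Criterion 6 bars SSRIs and SNRIs, "except duloxetine up to 60mg/day, escitalopram up to 10mg/day, or citalopram up to 20mg/day". In section 3.6.3, the QT column of Table 3 says of citalopram: "Dose-dependent QT prolongation".

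Section 3.6.1 is worded more broadly than criterion 3: "Subjects with QTc>450msec or any arrhythmia will be excluded". It then says that potential subjects at "elevated risk of developing ondansetron-associated arrhythmia (e.g., current use of QT-prolonging medication) are ineligible for this study".

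A heart-rate limit appears in two places, sections 3.2 (dose-limiting toxicity) and 3.3 (withdrawal). Both give sustained heart rate below 40 or above 120 beats per minute.

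**The concern.** The sentence in 3.5.4 is a statement of risk mitigation. It tells the IRB, the FDA and the DSMB that named high-risk groups will not be dosed, for a drug with an FDA communication on QTc given together with an experimental inhibitor. If the criteria that staff screen from do not carry out that statement, a patient whom the risk section describes as excluded can be enrolled under the list.

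Two things are at stake. One is who is dosed. The other is consistency: with no heart-rate cut-off at entry, two screeners could decide differently about the same patient with a slow sinus rate.

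**Working it through.** No sample size, power or error-rate figure is involved, so the check is a comparison of texts.

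**Step 1. Match each risk group in 3.5.4 to the numbered list.**

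| Risk group in 3.5.4 | Criterion | Covered? |
|---|---|---|
| Congenital long QT syndrome | 3 | Yes |
| Congestive heart failure | 4 | Yes |
| Bradycardias (unqualified) | 3, arrhythmia limb | Only if the rhythm is not sinus |
| QT-prolonging drugs | 11 | Yes, except that criterion 6 admits citalopram up to 20 mg/day |

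Two of the four groups are fully covered and two are covered in part.

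**Step 2. Bradycardia.** Sinus bradycardia is a sinus rhythm, so the parenthesis in criterion 3 leaves it out. None of the 11 numbered exclusions names bradycardia or gives a heart rate. The ECG checks do not close the gap. Section 2.4.2 describes the screening ECG only as a check on QTc, and section 2.4.3 describes the ECG before the second infusion as a check on QTc and sinus rhythm. Take an assumed patient in sinus rhythm at 45 beats per minute with a QTc of 430 ms. This patient passes criterion 3, passes both ECG checks, and does not meet the below-40 withdrawal limit. Read literally, 3.5.4 says that the patient is excluded.

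**Step 3. Citalopram.** Criterion 6 allows up to 20 mg/day, which section 3.6.3 explains as half of the approved maximum (0.5 × 40 = 20). Criterion 11 and 3.6.1 bar QT-prolonging drugs without any exception. For a patient on 20 mg/day, the list allows the drug in one criterion and, on Table 3's own description, bars it in another. Table 3 reports no clinically relevant QT prolongation for escitalopram or duloxetine, so among the three permitted antidepressants the issue is confined to citalopram.

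**Step 4. Where a heart-rate limit can act before dosing.** The plan allows up to 1 + 1 + 2 × (1 + 1) = 6 pre-dose readings per participant: screening vital signs and ECG, then pre-infusion vital signs and baseline ECG at each of two sessions. This is an upper count. Screening may fall on the morning of the first session, and heart rate is inferred from pulse oximetry and the 3-lead ECG. Section 3.3 is not limited to readings after infusion, so its limit covers at least the 2 readings at session 2 and arguably all 4 session readings. It is not stated as a rule for the 2 screening readings, which decide entry.

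**The case against.** The strongest reply is that the texts agree if bradycardias and arrhythmia mean only non-sinus rhythm disorders throughout. Criterion 3 defines arrhythmia that way, the repeat ECG checks for sinus rhythm, and 3.5.4 lists bradycardias among comorbidities, which suits diagnosed rhythm disorders better than an incidental slow rate. Section 3.6.1 may then be only a restatement of the criteria. This reading is possible, but no section states it, and it does not help with citalopram.

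A reader might infer more than the documents support, in three ways:

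- **That the protocol sets two conflicting entry standards for sinus bradycardia.** That is one reading of 3.6.1. The protocol does place other entry rules outside the numbered list (the opioid dose limit in 2.4.2, bleeding history and laboratory results in 3.6.4), so 3.6.1 may be binding. That is an argument by analogy.
- **That no heart-rate limit operates before dosing.** Section 3.3 can withdraw a participant with a sustained rate below 40 before the second infusion.
- **That tariquidar is shown to slow the heart at this dose.** Section 3.5.5 reports one bradycardia case in a 4 to 8 mg/kg study, without its dose, and one at 8 mg/kg in another study; this trial uses 4 mg/kg. The same section says that heart rate and ECG did not change significantly in the first of those studies. In section 2.2, the largest mean heart-rate change with tariquidar in the first 8 participants was an increase of 12.1 beats per minute. Section 3.5.4 adds that none of 15 subjects given 16 mg ondansetron under the same criteria had an arrhythmia.

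The citalopram choice is disclosed, reasoned and dose-capped in 3.6.3. What stands is that criterion 11, 3.5.4 and 3.6.1 do not mention the exception.

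**Conclusion.** The statement in 3.5.4 is wider than the criteria it relies on. Sinus bradycardia is not excluded by the numbered list, and citalopram up to 20 mg/day is allowed despite the bar on QT-prolonging drugs. Section 3.6.1 might fill the first gap but supplies no threshold, and the limit in 3.2 and 3.3 is not an entry rule.

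This rests on reading bradycardias in 3.5.4 as written, without a qualifier, and on Table 3's own description of citalopram. The number of patients affected cannot be estimated from the documents. The QTc limit, the heart-failure exclusion, ECG monitoring to 2 hours after infusion and the QTc withdrawal rules all remain. This is a minor safety and eligibility correction, with no effect on endpoints, sample size or analysis.

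**What to change.** Add bradycardia, with a resting heart-rate cut-off set by the sponsor, to criterion 3 in the synopsis and in 2.3.3. The documents give no entry value, so the sponsor has to choose one. Apply it at the existing screening ECG and at the ECG before the second infusion, and use the same wording in 3.6.1. State the citalopram allowance as an explicit exception in criterion 11, 3.5.4 and 3.6.1.

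If the sponsor intends patients with sinus bradycardia to be eligible, 3.5.4 should say so and 3.6.1 should match criterion 3. That would only correct the wording and would not provide the protection that 3.5.4 now claims.

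The cost is one wording amendment and no new procedure. The downside is a few extra screen failures, and the loss after one session of any participant who first falls below the cut-off before the second infusion. Section 3.3 already provides for replacement, and the planned enrolment of 28 to 32 leaves room for up to 32 − 28 = 4 non-evaluable participants from all causes.

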3.5.5 Potential risks from tariquidar

Tariquidar is an experimental drug, a specific 3rd generation inhibitor of P-glycoprotein, currently in development by Avaant Pharmaceuticals Inc. In a Phase I study in healthy volunteers, intravenous tariquidar doses in the range of 0.1-2mg/kg did not cause any adverse effects.⁴¹

In healthy volunteers, a 2mg/kg intravenous dose resulted in no serious adverse effects. Two of ten subjects receiving this dose developed mild metallic taste during tariquidar infusion. Two subjects who received a 4mg/kg dose experienced light-headedness and conjunctival infection. One subject developed a brief syncopal episode after a PET-scan procedure, resolved without sequelae. A 6mg/kg intravenous dose resulted in mild metallic taste and nausea that resolved after the infusion was stopped.⁴²

In healthy volunteers receiving 4, 6 or 8mg/kg intravenous tariquidar doses, no serious adverse events have been observed.⁴³ Overall, four cases of hematoma and one case of phlebitis due to cannulation, as well as five cases of metallic taste in the mouth occurred. Other adverse drug effects to tariquidar were vertigo (two), bradycardia (one) and headache (one). Heart rate, blood pressure as well as ECG did not significantly change during and after tariquidar administration. No subject had any significant change in blood chemistries (including electrolytes, liver and renal function tests), complete blood count and coagulation over the whole study period. No volunteer discontinued prematurely the study. In one case, for safety reasons the infusion was stopped 20 min before the scheduled end due to moderate orthostatic hypotension and vertigo.⁴³

In an additional healthy volunteer study testing intravenous tariquidar doses in a range of 3-8 mg/kg, adverse events possibly/probably related to tariquidar included 1) dysgeusia (changes in the sense of taste) in 6/20 subjects, across 3mg/kg, 4mg/kg, 6mg/kg and 8 mg/kg doses; 2) vertigo in 3/20 subjects receiving 3mg/kg (n=1) and 8mg/kg (n=2) doses; 3) headache (n=1, 6mg/kg dose); and 4) hypotension and bradycardia (n=1, 8mg/kg; infusion stopped after 7.2mg/kg was infused).

Seven clinical studies of the pharmacokinetics and efficacy of tariquidar have been completed in cancer patients. The main use of tariquidar in these clinical trials has been to enhance BBB-penetration and tumor-penetration of Pgp-substrate chemotherapy agents, to improve the efficacy of cancer chemotherapy. In these studies, tariquidar have been shown to increase the severity of known side effects of chemotherapeutic agents, including hematological abnormalities such as anemia and thrombocytopenia. No additional side effects other than those known to be associated with chemotherapy have been identified in patients who have received tariquidar (Tariquidar Investigator's Brochure).

Each ampoule of Tariquidar for injection contains 10 mL of 7.5 mg/mL tariquidar (as the dimesylate salt, in a sterile solution of 20% ethanol/80% propylene glycol with a small amount of hydrochloric acid) for a total of 75 mg tariquidar free base per ampoule. Ampoules will be stored refrigerated (2-8°C) and protected from light. Within 4 hours prior to administration, the tariquidar solution will be diluted aseptically by the Washington University Investigational Drug Service with 5% dextrose in water (D5W) to give a final volume of 250 mL. The diluted solution will be protected from light until infusion is complete.

3.5.7 Potential risks from thermal testing

Risk of injury related to thermal pain testing is minimal. Thermal testing is widely used and considered safe. While thermal testing does produce pain, risks to the individual are minimal, because 1) the pain is transient in nature and generally subsides immediately after the procedure; 2) subjects are instructed that they may stop any procedure at any time with no adverse consequences; and 3) the level of pain experienced by subjects is below their tolerance level. With thermal stimulation there is a very slight risk of a burn, but this is minimized by the following: 1) positive lockout of stimulus parameters above 52°C; and 2) the stimulator has built in a shut-down system to prevent the delivery of prolonged or high intensity stimuli. The TSA-II thermal devices have FDA 501(k) clearance (K922052). CPM testing is conducted using an ice water bath at 8°C and exposure is limited, thereby posing minimal risk of tissue damage from cold exposure.

